4.4.7 Compliance

Compliance to treatment will be assessed by evaluating the DFP solution volume in each medicine bottle or the number of DFX dispersible tablets in the blister pack remaining at each visit.

DFP used volume will be evaluated measuring the difference between the intact bottle volume (250 ml) and the remaining volume in the returned bottle.

4.4.8 Quality of Life

Child Health Questionnaire™ (CHQ) will be assessed to evaluate the Health Related Quality of Life (HRQoL) from the point of view of parents or guardians. CHQ is 28 items generic quality of life instrument designed and normed for children 5-to-18 years of age (**Annex 2**).

CHQ will be completed at baseline, at month 6 (V9) and after 12 month of treatment in the subgroup of the experimental population for which the questionnaire is validated (5-to-18 years of age).

5. SELECTION AND ENROLLMENT OF SUBJECTS

The study population includes 388 iron chelator naïve and not naïve patients affected by hereditary haemoglobinopathies (including but not limited to thalassaemia syndromes and SCD) and requiring chronic transfusion and chelation therapy.

Patients of both genders aged from 1 month to less than 18 years will be recruited. At least 10% of the patients will be from 1 month to less than 6 years of age.

Patients meeting inclusion/exclusion criteria as outlined in **Section 5.1** and in **Section 5.2** will be enrolled.

5.1 Inclusion criteria

Patients will be eligible for inclusion in this study if the following criteria apply:

- patients of both genders aged from 1 month up to less than 18 years at the time of enrolment
- patients affected by any hereditary haemoglobinopathy requiring chronic transfusion therapy and chelation, including but not limited to thalassemia syndromes and sickle cell disease
- patients
 - on current treatment with DFO or DFX or DFP in a chronic transfusion program receiving at least 150 mL/kg/year of packed red blood cells (corresponding approximately to 12 transfusions)
 - naïve to chelation treatment who have received at least 150 mL/kg of packed red blood cells (corresponding to approximately 12 transfusions) in a chronic transfusion program and with serum ferritin levels \geq 800 ng/mL at screening
- Until availability of results from the PK Study (Study DEEP-1, EudraCT n. 2012-000658-67) for patients aged from 1 month to less than 6 years: known intolerance or contraindication to DFO
- written informed consent obtained from patient's legal guardian in accordance with the national legislations. Patient's informed assent will be collected according to his/her maturity and understanding.

5.2Exclusion criteria

A patient will not be eligible for inclusion in this study if any of the following criteria apply:

- patients with known intolerance or contraindication to either DFP or DFX
- patients receiving DFX at a dose > 40 mg/kg/day or DFP at a dose > 100 mg/kg/day at screening
- platelet count <100.000/mm³ at the wash-out visit (day -7)
- absolute neutrophil count <1.500/mm³ at the wash-out visit (day -7)
- Hb levels lower than 8g/dL at the wash-out visit (day -7)
- Evidence of abnormal liver function (ALT level >5xULN) at screening
- iron overload from causes other than trasfusional haemosiderosis
- severe heart dysfunction secondary to iron overload defined as the occurrence of heart failure or severe arrhythmia or cardiac MRI T2* lower than 10 ms available
- serum creatinine level > ULN for age at the wash-out visit (day -7)
- history of significant medical or psychiatric disorder
- the patient has received another investigational drug within 30 days prior to consent to study participation
- fever and other signs/symptoms of infection at the wash-out visit (day -7)
- concomitant use of trivalent cation-dependent medicinal products such as aluminium-based antacids
- positive test for β-HCG or lactating female patients.

5.3Study Enrolment Procedures

Patients meeting the inclusion/exclusion criteria will be randomized on Day 0 of the study, at a 1:1 ratio to one of the two groups of 194 patients (see **Section 6.6** for details on randomisation). One group will be treated with DFP, the other (control) group with DFX.

Informed consent will be requested to parents/legal guardians. Assent will be requested to children of a maturity sufficient to understand and capable of forming an opinion on the information provided, as stated in "Ethical Considerations for Clinical Trials on Medicinal Products conducted with the Paediatric Population – Recommendations of the Ad Hoc Group for the development of implementing guidelines for Directive 2001/20/EC relating to GCP in the conduct of clinical trials on medicinal products for human use" (2008, EudraLex Vol. 10 Chapter V). For further details, please refer to **Section 7.3.1**.

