3.3 Interventional drugs

Deferiprone is the experimental drug.

Deferiprone will be administered orally at the approved dosage of 75-100mg/kg/day for 7 days per week for the entire duration of the treatment (12 months).

For children from 1 month to less than 6 years, where limited data are available in the SmPC and in literature, the dosage will be derived by the results of an *ad hoc* designed Pharmacokinetic (PK) study sponsored by the same DEEP Consortium (Study DEEP-1, EudraCT n. 2012-000658-67).

The deferiprone formulation to be used in this trial is a new strength (80 mg/mL) of the currently marketed DFP oral solution (Ferriprox® 100 mg/mL oral solution), with some changes in excipients. This lower strength formulation was recently developed by the Marketing Authorisation Holder (MAH) and included in an approved Paediatric Investigational Plan (PIP), and will allow the administration of more accurate volumes in children, minimising the risk of over- or under-dosing. This formulation will also provide the advantage of improved palatability, thus ameliorating objections to the inherently bitter taste of the currently available syrup. Thus, it is expected to improve patients' compliance, and thereby clinical outcomes and quality of life (QoL). For further details please refer to **Section 6.1**.

Deferasirox (Exjade®) is the comparator.

DFX dosage will range from 20 to 40 mg/kg/day as recommended in the SmPC currently approved in Europe (**Annex 1**). For further details please refer to **Section 6.2**.

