The target patient population consists of 388 outpatients affected by hereditary haemoglobinopathies requiring chronic transfusion and chelation, randomized 1:1 in two groups of 194 patients each to ensure 310 evaluable patients. Chelation naïve and not naïve patients aged from 1 month to less than 18 years will be recruited. A staggered approach will be applied to patients aged less than 6 years (10% of the total sample), which will be recruited after results from the PK Study (Study DEEP-1, EudraCT n. 2012-000658-67) will be available.

Experimental arm: patients administered with DFP at 75-100 mg/kg/day for seven days per week. In patients aged less than 6 years the dose will be defined according to the results of the PK Study (Study DEEP-1, EudraCT n. 2012-000658-67). DFP daily dose will not exceed 100 mg/kg.

Control arm: patients administered with DFX at 20-40 mg/kg/day as recommended by the currently approved European SmPC (last update 10/08/2011). DFX daily dose will not exceed 40 mg/kg.

Details on the starting dose and subsequent dose adjustments are reported in **Section 6**.

The **treatment duration** for both groups is 12 months.

4.1Non-inferiority margin

This study is designed to demonstrate the **non-inferiority** of a new liquid DFP (80 mg/mL) formulation in comparison with DFX in terms of percentage of successfully chelated patients as described in **Section 4.3**.

DFP will be declared non inferior to DFX if the lower limit of the 95% confidence interval for the difference in the proportion of successful chelation in the two groups is above -12.5%. The choice of this margin is based on clinical considerations starting from the available evidences for the effects of DFX at both ferritin and cardiac levels. For details please refer to **Section 11**.

4.2Choice of comparator

DFP will be compared to the oral chelating agent DFX. The rationale for comparing two oral chelators derives from the recent literature data reporting that oral chelating agents currently represent the most widespread adopted therapy in the paediatric age, due to good compliance, improved QoL and reduced burden of the disease (Ceci A et al, 2011).

4.3Primary endpoint

The primary endpoint will be the measure of treatment efficacy defined as the percentage of patients successfully chelated, as assessed by serum ferritin levels (in all patients) and cardiac MRI T2* (in patients above 10 years of age able to have an MRI scan without sedation).

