6. INVESTIGATIONAL MEDICINAL PRODUCTS

6.1 Deferiprone

Patients will be enrolled in the experimental arm at the DFP starting dose of 75 mg/kg/day or at their ongoing DFP dosage as long as this does not exceed 100 mg/kg/day.

In patients aged less than 6 years the initial dose will be defined according to the results of the PK study (Study DEEP-1). DFP should be taken daily 3 times-a-day: after breakfast, after lunch and after dinner, preferably at consistent times.

The investigational drug is provided as 80 mg/mL oral solution packaged in 250 mL amber polyethylene terephthalate bottles with threaded neck. White polypropylene child-resistant caps with foam liners have been used as closures.

An administration device that facilitates accurate measurement of appropriate dose volumes is provided. Since the formulation is intended for the entire paediatric group, two distinct administration devices (CE marked) will be provided: a graduated syringe (10 mL in steps of 0.2 mL) and a graduated measuring cup (30 mL in steps of 2.5 mL).

The patient, or the legal guardian of the patient, will be explained how to compose the patient's personal daily dose.

The total daily dose of DFP and the exact volume of solution per day will be calculated by the investigator based on the patient's body weight through the following formula:

$$\text{Total daily volume (mL)} = \frac{\text{dose level (mg/kg/day)} \times \text{body weight (kg)}}{80 \text{ mg/ml}}$$

Each administered dose is the total daily volume divided by three.

Every month, during the regular visits, the investigator will hand out an appropriate number of drug bottles to the patient and/or the legal guardian. Each bottle dispensed will be unambiguously characterized by the investigator through entering subject identifier and visit # on the provided space on drug label. The exact volume, the bottle identifier and the date of dispensation will be recorded in the Case Report Form (CRF). Medication returned by the patient will be counted and unused volumes will be tracked as well.

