Protocol No. DEEP-2

(deferasirox) are covered by the trial in those countries in which no facilities are provided, thus allowing children to benefit from the oral chelating agent.

Specific benefits are expected for a particularly vulnerable subgroup of the experimental population, namely children from 1 month to less than 6 years. These patients will be enrolled in the trial only after the availability of results identifying the most suitable dose and dosing regimen of DFP in this age group as derived from the PK study (Study DEEP-1, EudraCT n. 2012-000658-67).

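### The Section 5.1 entry condition for under-6s implies early entry that Sections 4 and 20 forbid and for which no deferiprone dose is defined

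*Combined protocol and SAP*

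**What the plan says.** The inclusion criterion in Section 5.1 has two parts. The first sets its period and age group: "Until availability of results from the PK Study (Study DEEP-1, EudraCT n. 2012-000658-67) for patients aged from 1 month to less than 6 years". The second sets its content: "known intolerance or contraindication to DFO". Nothing in Section 5.1 or 5.2 says that under-6s must wait for DEEP-1, and the first criterion in 5.1 admits patients from 1 month of age.

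The waiting rule is stated elsewhere. Section 4 describes a staggered approach for patients under 6, "which will be recruited after results from the PK Study". Section 20 says of the same children: "These patients will be enrolled in the trial only after the availability of results identifying the most suitable dose".

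On dose, Section 6.1 says: "In patients aged less than 6 years the initial dose will be defined according to the results of the PK study". Sections 3.3 and 4 also refer the under-6 dose to DEEP-1. The one fixed figure is in Section 4: "DFP daily dose will not exceed 100 mg/kg".

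On who enters, Section 5 states its rule as "Patients meeting inclusion/exclusion criteria as outlined in" Sections 5.1 and 5.2, and says that these patients will be enrolled. Section 5.3 has those who meet the criteria randomised on Day 0. Section 7.3.3 requires the criteria to be satisfied at the wash-out visit (V2, day -7).

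**The concern.** A time-limited entry condition makes sense only if entry is possible during that time. Anyone working from the eligibility list would take this one to mean that, before DEEP-1 reports, a child under 6 who cannot take DFO may enter, and that other under-6s may not. Sections 4 and 20 allow neither.

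The gate exists because the DFP dose for this age group is not yet known. Section 20 calls these children particularly vulnerable and presents waiting for the dose as a benefit to them. A child admitted under 5.1 in that period would be enrolled against Sections 4 and 20. If allocated to DFP, the child would reach Day 0, when treatment must start, with no dose level to put into the volume formula of Section 6.1.

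**Working it through.** The point turns on text, so the check sets the sections side by side for a child under 6 with known DFO intolerance who meets every other criterion.

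| Question | Before DEEP-1 reports | After DEEP-1 reports |
|---|---|---|
| Sections 5.1/5.2, applied as Sections 5, 5.3 and 7.3.3 direct | Enrolled and randomised | Enrolled and randomised; the DFO condition has lapsed |
| Sections 4 and 20 | Not recruited, no exception | May be recruited |
| DFP dose (3.3, 4, 6.1) | None; ceiling of 100 mg/kg/day only | Set from DEEP-1 |
| DFX starting dose (6.2, Table 3) | Defined | Defined |

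1. In the first column the first two rows cannot both be followed as written. If Sections 4 and 20 govern, the 5.1 condition never operates. If 5.1 governs, Sections 4 and 20 are breached.
2. The general DFP start in Section 6.1 (75 mg/kg/day, or the ongoing dose) does not fill the gap. It is followed by a separate rule for under-6s that points to DEEP-1. A ceiling is not a dose.
3. Reading the criterion as a DFO condition on patients of all ages until the under-6 results arrive does not rescue it. Section 5.1 expressly admits patients currently treated with DFO.
4. Section 6.6 stratifies at age 10 and describes no hold at age 6, so the documents show no step at randomisation that would stop such a child.

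**Period at risk.** The protocol gives no DEEP-1 reporting date. Section 7.1 limits recruitment to 12 months. The period is 0 months if DEEP-1 reports before the first patient, and under the plan it must be shorter than 12. Section 5 requires at least 10% of patients to be under 6: 0.10 × 388 = 38.8, so at least 39 children. Under Sections 4 and 20 all of them enter after DEEP-1. A 12-month wait would leave that floor unmet.

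**Time off chelation.** Wash-out runs from day -6 to day -1, which is 6 days, for every patient already on a chelator, and 0 days for a chelation-naive child (Section 7.2.1). The part specific to this conflict is any delay after Day 0. The documents give no basis for its length.

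**Sample size.** The inputs in Sections 11.6 and 11.12 are success rates of 65% (DFX) and 67.5% (DFP), a margin of 12.5 points, one-sided 0.025 and 80% power. Per arm, (1.960 + 0.842)² × (0.65 × 0.35 + 0.675 × 0.325) / (0.125 + 0.025)² ≈ 156, or 312 in total against the stated 310. Dropout inflation gives 310 / 0.80 = 387.5, or 388 as stated. None of these inputs depends on when under-6s enter.

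**The case against.** The best defence is that the criterion only narrows entry. Adding a restriction is not granting permission, and a site that reads the whole protocol can satisfy every section by enrolling no under-6 early. The gate is stated twice, three sections tie the DFP dose to DEEP-1, and the criterion itself names DEEP-1, which should alert the reader. There are also chances to catch the problem before Day 0: the review of the protocol with investigators before initiation (Section 13), the consent discussion (7.3.2), sponsor supply of DFP (6.4) and central randomisation (6.6).

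Much of this stands as to likelihood. Misuse needs a site to apply 5.1 and 5.2 without regard to Sections 4, 6.1 and 20, and the safeguards make early detection plausible, although none is described as a hold at age 6. It does not remove the contradiction. Section 5 does not treat 5.1 and 5.2 as one filter among several; it says that patients who meet them will be enrolled. On those terms a DFO-intolerant child under 6 qualifies before DEEP-1 reports.

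A second objection is that rewriting the criterion would delete a DFO safeguard. It would not: the condition as written already lapses when DEEP-1 reports, which is when Sections 4 and 20 first admit these children.

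**Conclusion.** The concern holds: Section 5.1 is wrong as written. It implies early entry for some under-6s, against an unqualified bar in Sections 4 and 20 and with no DFP dose to give them. The size is small or unknown. The number of children affected may be zero, and the documents support no upper estimate. The consequence is a protocol deviation and, for a child allocated to DFP only, delayed chelation after Day 0. This rests on some sites working from the eligibility list, and on DEEP-1 not having reported when recruitment opens.

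A reader might infer more, and the documents do not support it:

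- *That children would be given an undefined dose.* Without a dose level the Section 6.1 formula cannot be completed, so the likelier result is a query and a delay.
- *That the 6 days of wash-out are harm caused by this conflict.* Every pre-treated patient has them.
- *That the exposure lasts up to 12 months.* That would mean the under-6 floor had already failed.
- *That the trial's conclusions are affected.* Analysis, sample size and power do not change.

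**What to change.** Replace the criterion in Section 5.1 with: *patients aged 1 month to less than 6 years are eligible only after the DEEP-1 results are available and the DFP dose for this age group is defined*. This puts the existing gate where eligibility is decided.

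In the same amendment the sponsor should decide whether the DFO condition should apply after DEEP-1. Section 3.1 describes DFX as authorised under 6 years when DFO is contraindicated, yet the condition ends just as under-6s can first be randomised to DFX. If it is kept, state it in 5.1 without a time limit, and allow for the fact that it narrows the pool from which at least 39 under-6s must come. If early entry was really intended, Sections 4 and 20 must be amended instead and an interim under-6 dose given in Section 6.1.

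The cost of the basic change is one criterion of wording, plus ethics approval and, in some countries, regulatory approval under Section 18.2. Procedures, sample size and analysis stay as they are.

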6. INVESTIGATIONAL MEDICINAL PRODUCTS

6.1 Deferiprone

Patients will be enrolled in the experimental arm at the DFP starting dose of 75 mg/kg/day or at their ongoing DFP dosage as long as this does not exceed 100 mg/kg/day.

In patients aged less than 6 years the initial dose will be defined according to the results of the PK study (Study DEEP-1). DFP should be taken daily 3 times-a-day: after breakfast, after lunch and after dinner, preferably at consistent times.

The investigational drug is provided as 80 mg/mL oral solution packaged in 250 mL amber polyethylene terephthalate bottles with threaded neck. White polypropylene child-resistant caps with foam liners have been used as closures.

An administration device that facilitates accurate measurement of appropriate dose volumes is provided. Since the formulation is intended for the entire paediatric group, two distinct administration devices (CE marked) will be provided: a graduated syringe (10 mL in steps of 0.2 mL) and a graduated measuring cup (30 mL in steps of 2.5 mL).

The patient, or the legal guardian of the patient, will be explained how to compose the patient's personal daily dose.

The total daily dose of DFP and the exact volume of solution per day will be calculated by the investigator based on the patient's body weight through the following formula:

$$\text{Total daily volume (mL)} = \frac{\text{dose level (mg/kg/day)} \times \text{body weight (kg)}}{80 \text{ mg/ml}}$$

Each administered dose is the total daily volume divided by three.

Every month, during the regular visits, the investigator will hand out an appropriate number of drug bottles to the patient and/or the legal guardian. Each bottle dispensed will be unambiguously characterized by the investigator through entering subject identifier and visit # on the provided space on drug label. The exact volume, the bottle identifier and the date of dispensation will be recorded in the Case Report Form (CRF). Medication returned by the patient will be counted and unused volumes will be tracked as well.

6.2 Deferasirox

Patients will be enrolled in the control arm at a DFX starting dose which depends on patient current therapy at screening as summarised in **Table 3**.

Table 3. Starting dose for DFX arm

None (Naïve patient)	20 mg/kg body weight
Deferiprone	20 mg/kg body weight
Deferoxamine	Half DFO dose (but not less than 20 mg/kg body weight)
Deferasirox	Current patient's posology (but not higher than 40 mg/kg)

For all naïve patients and patients on DFP at screening the starting DFX dose will be 20 mg/kg body weight. If the patient's chelation therapy at screening is DFO, the starting dose of DFX will be numerically half that of the DFO dose (e.g. a patient receiving 40 mg/kg/day of DFO for 5 days per week (or equivalent) could be transferred to a starting dose of 20 mg/kg/day of DFX) but, in any case, to a starting dose not inferior to 20 mg/kg/day.

If the patient's chelation therapy at screening is DFX, the patient starting dose of DFX will be his/her current posology as long as this does not exceed 40 mg/kg.

An initial dose of 30 mg/kg will be allowed for patients who require reduction of elevated body iron levels (defined as serum ferritin level > 2500 ng/ml or MRI T2* < 20 ms).

DFX tablets will be available at dosage strengths of 125 mg, 250 mg and 500 mg DFX, in re-labelled commercial packs containing dispersible tablets in PVC/PE/PVDC/Aluminium blisters.

The individual daily doses of DFX and the tablets composition contributing to the daily dose will be calculated by the investigator based on the patient's body weight through the following formula:

Total daily dose (mg) = dose level (mg/kg/day) × body weight (kg)

Doses must be rounded to the nearest whole tablet size as recommended in the Exjade® SmPC (**Annex 1**).

DFX must be taken once a day on an empty stomach at least 30 minutes before food, preferably at the same time each day. The tablets can be dispersed by stirring in a glass of water or orange or apple juice (100 to 200 mL) until a fine suspension is obtained. Dispersion in carbonated drinks or milk is not recommended.

After the suspension has been swallowed, any residue must be re-suspended in a small volume of water or juice and swallowed. The tablets must not be chewed or swallowed whole.

